In Aim 1, we will determine whether individuals with PTSD have higher levels of activated microglia compared to trauma-exposed control subjects as measured with [C]PBR28 PET brain imaging. Eighty subjects (n=40 with a primary diagnosis of PTSD; n=40 trauma-exposed controls) will participate in a [C]PBR28 PET scan to assess baseline levels of activated microglia. We will perform clinical assessments and measure cytokine levels, mood, anxiety and neurocognitive function on PET scan day. *Based on our preliminary data, we hypothesize that individuals with PTSD will have higher levels of neuroinflammation compared to trauma-exposed healthy controls, particularly in the amygdala, hippocampus, ventral striatum and frontal cortex, and that higher levels of neuroinflammation will be associated with greater severity of mood and anxiety symptoms and neurocognitive dysfunction.* 

In Aim 2, we will use our novel neuroinflammation "stress test" to determine whether individuals with PTSD vs. trauma-exposed controls have a dysfunctional neuroinflammatory response to systemic administration of LPS. The same subjects from Aim 1 will be administered LPS 3 h prior to a second [C]PBR28 PET scan on the same day, consistent with our established paradigm(13). Cytokine and cortisol levels, mood and anxiety symptoms, and neurocognitive function will be assessed pre- and post-LPS administration. *We hypothesize based on preclinical studies(16) that, compared to controls, individuals with PTSD will have an exacerbated neuroimmune response to LPS evidenced by greater increases in activated microglia. We further expect that greater LPS-induced increases in activated microglia will be associated with greater increases in cortisol levels, mood and anxiety symptoms, and reductions in neurocognitive function.* 

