Linear mixed-effects models will be used to compare LPS-induced changes in [C]PBR28  $V_T$  values in the Trauma Control and PTSD groups. Group (Control vs. PTSD) and rs6971 polymorphism in the TSPO gene will be entered as fixed factors, subject as a random effect, pre-LPS global [C]PBR28  $V_T$  values as a covariate, and post-LPS global [C]PBR28  $V_T$  values as the dependent variable; variables that differ between Trauma Control and PTSD groups will be entered as additional fixed factors (categorical variables) or covariates (continuous variables). An ANCOVA with the rs6971 polymorphism in the TSPO gene and other variables that differ by PTSD status entered as covariates will be conducted to compare %change in [C]PBR28  $V_T$  values in the PTSD vs. Trauma Control group. Post-hoc analyses adjusted for multiple comparisons ( $\alpha$ =0.005; 0.05/10 brain regions) will be conducted to evaluate LPS-induced changes in [C]PBR28  $V_T$  values in individual brain regions in these two groups. Interrelationships among changes in outcome measures will be evaluated in the full sample and by PTSD group status using parallel process analyses in Mplus version 7.31.

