Partial correlations adjusted for the rs6971 polymorphism will be conducted to examine associations between baseline and LPS-induced measures of global [C]PBR28  $V_T$  values, peripheral inflammatory markers, and endophenotypic and phenotypic measures of threat, loss, and neurocognitive function. Associated peripheral inflammatory markers will then be entered into a bias-corrected bootstrap test of mediation to evaluate whether global [C]PBR28  $V_T$  values mediate the relation between peripheral inflammatory markers, and measures of threat and loss symptoms, and neurocognitive function. A parallel set of tests of mediation will be conducted to examine whether LPS-induced increases in activated microglia mediate the relation between LPS-induced increases in peripheral inflammatory markers and the measures of threat and loss symptoms, and neurocognitive function. In this analysis, LPS-induced changes in peripheral inflammatory markers will be modeled as the independent variable, percent change in global [C]PBR28  $V_T$  values as the mediator variable, and LPS-induced changes in threat and loss symptoms and neurocognitive function as dependent variables. These tests employ a non-parametric bootstrapping procedure (10,000 samples) to generate estimates of direct and indirect effects, and confidence intervals(125-127). SECTION II: RESEARCH INVOLVING DRUGS, BIOLOGICS, RADIOTRACERS, PLACEBOS AND DEVICES

If this section (or one of its parts, A or B) is not applicable, check off N/A and delete the rest of the section.

[figure not shown]

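### The Aim 3 LPS mediation model uses change in marker, percent change in global VT and change in symptoms or cognition with no pre-LPS covariates, so correlated starting levels can create or hide an indirect effect

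*Combined protocol and SAP*

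**What the plan says.** Section I, item 13 (Statistical Considerations) describes Aim 3 in its last paragraph. A first step screens associations: "Partial correlations adjusted for the rs6971 polymorphism will be conducted to examine associations between baseline and LPS-induced measures of global" VT, peripheral markers and the clinical measures. Markers that show an association then go into a "bias-corrected bootstrap test of mediation" with 10,000 resamples.

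For the LPS part the three variables are:
- **Independent variable:** "LPS-induced changes in peripheral inflammatory markers will be modeled as the independent variable".
- **Mediator:** "percent change in global" VT.
- **Outcome:** "LPS-induced changes in threat and loss symptoms and neurocognitive function as dependent variables".

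No covariate is listed for this model. The rs6971 adjustment is stated only for the screening correlations. VT is fixed as a percent change; the scale of the marker and symptom changes is not given.

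Two other places matter. The Aim 2 paragraph of the same item specifies a mixed model with "subject as a random effect, pre-LPS global" VT as a covariate, so baseline adjustment is used there and not carried over. In Section I, item 1, Aim 1 states that "higher levels of neuroinflammation will be associated with greater severity of mood and anxiety symptoms and neurocognitive dysfunction", and Aim 3(a) expects higher baseline markers to go with higher baseline VT and worse symptoms.

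**The concern.** A change usually depends on the level it started from. If LPS adds a roughly fixed amount to VT, percent change is smaller in subjects with high pre-LPS VT. Symptom change may be smaller in subjects who start high on a bounded scale, or larger if severe subjects are sensitised. When pre-LPS VT and pre-LPS symptoms are themselves correlated, as the protocol expects, the two changes become associated through baseline even if the VT response has no effect on the symptom response.

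The path from VT change to symptom change carries the Aim 3(b) claim. Without the starting levels in the model, that path mixes a response-to-response link with the cross-sectional link already studied under Aims 1 and 3(a). A positive result could restate the baseline relation, and a real effect could be cancelled. The partial correlations among LPS-induced measures share the weakness.

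**Working it through.** The plan gives no power or error rate for the mediation test, so there is no figure of its own to reproduce. The check asks how often the test declares mediation when VT change has no effect on symptom change.

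**Inputs from the documents**
- n = 80 (40 + 40) and pre/post correlation 0.50 for VT (Sample Size Calculation).
- LPS effect on VT of 31% to 63% (same section).
- VT spread, implied by difference divided by d: 21.5/1.02 = 21% of the mean and 8.8/0.38 = 23%.
- Baseline VT with cognition: r = -0.47 and -0.39 (Preliminary studies, d). A group difference of d = 0.80 to 1.02 in equal groups gives r = d/√(d²+4) = 0.80/√4.64 = 0.37 to 1.02/√5.04 = 0.45 between VT and group. Because groups are defined by PTSD status, the design itself tends to tie baseline VT to baseline symptoms.

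**Assumed, because the documents do not say:** the baseline VT-symptom correlation r0, the correlation rS of symptom change with its own baseline, and whether the LPS increment is additive or proportional.

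**Why baseline matters**
1. With an additive increment of 46% of the mean and a VT SD of 21%, a subject one SD above the mean changes by 46/1.21 = 38% and one SD below by 46/0.79 = 58%. With a proportional increment both change by 46%.
2. With equal pre and post variances and pre/post correlation ρ, a raw change correlates -√((1-ρ)/2) with its baseline, which is -0.50 at ρ = 0.50. Taking rS = -0.5 for symptoms borrows this VT planning value.
3. If responses given baseline are independent, two raw changes correlate r0(1-ρ)/2. At r0 = 0.47 and ρ = 0.50 this is 0.47 × 0.5/2 = 0.12, with no response-to-response link.

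**Simulation A: additive increment.** Within-genotype VT CV 21%, mean increment 46% (SD 10 points), scan error 7%, marker-to-VT-increment correlation 0.5, no VT-to-symptom effect, bias-corrected interval. The adjusted model adds pre-LPS VT and pre-LPS symptoms.

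| r0 | rS | Positive call, plan | Positive call, adjusted | Any call, plan | Any call, adjusted |
|---|---|---|---|---|---|
| 0.39 | -0.3 | 8.5% | 4.5% | 9.0% | 9.5% |
| 0.39 | -0.5 | 13.6% | 4.0% | 13.9% | 6.9% |
| 0.47 | -0.5 | 18% | 2-3% | not tabulated | not tabulated |
| 0.60 | -0.3 | 14.0% | 4.0% | 14.5% | 8.4% |
| 0.60 | -0.5 | 24.4% | 3.9% | 24.4% | 7.6% |

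Nominal is 2.5% for positive calls and 5% for any call. The first row rests on 400 trials (standard error about 1.5 points); a repeat gave 8% versus 4%. Other repeats of the additive design ran higher, up to 36% versus 3-6% adjusted at r0 = 0.60, so the figures are indicative. At r0 = 0 plan and adjusted agree (4% and 5%), which locates the excess in the correlated baselines.

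**Variations on A**
- Percentile interval, any direction, for the three settings run: 8.1%, 15.5% and 8.1% as planned; 4.3%, 4.7% and 4.9% adjusted. Part of the excess over nominal therefore belongs to the bias-corrected interval.
- Proportional increment, no effect: 6.4-9.8% as planned, 5.6-9.6% adjusted, so the baselines make no material difference.
- rS = +0.3: positive calls 1.1% as planned versus 3.5% adjusted. At r0 = 0.47, wrong-direction calls were 11% versus 2.5%.
- With a true link of 0.4: power 44.8% versus 47.7% adjusted (additive), 31.0% versus 37.3% (proportional). Adjustment cost no power.

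**Simulation B: a different model.** Post = ρ × pre + noise for all three variables, ρ = 0.50, VT SD 25% of the mean, LPS effect 45%, neither mediation path present. With percent change in VT, the bias-corrected test called mediation (either direction) in 1.3% at r0 = 0, 13% at 0.47 and 58% at 0.8; with all three baselines, 0.5% to 1.3%. With raw VT change the unadjusted figures were 2.0%, 7.3% and 22%. By a joint-significance test on percent change the rate at r0 = 0.47 was 9.1%, falling to 3.3% at ρ = 0.75; at r0 = 0.3 and ρ = 0.50 it was 2.3%.

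**The case against.** **The wording leaves room.** The Aim 2 paragraph also speaks of LPS-induced changes and then models post-LPS VT adjusted for pre-LPS VT. Marker and symptom changes in Aim 3 could be meant the same way. This stands as an ambiguity, but VT is explicitly a percent change and no covariate is named.

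**Another analysis may cover it.** The Aim 2 paragraph plans parallel process models in Mplus for linked changes, and such models commonly include initial level. The plan neither states those terms nor ties them to the mediation test, so this is partial cover at most.

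**The size rests on assumptions.** The documents report LPS effects only as percentages, and the background's priming hypothesis points away from a purely additive increment. Under a proportional increment the problem disappears, and even the sign of the symptom dependence is unknown. This stands in full.

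**Screening may protect.** If a marker enters only when its change correlates with symptom change, false mediation was at most 1.2% in runs where the marker had no direct effect on symptoms. Once it had one, the rates were 18% as planned and 3% adjusted. If only a marker-VT association is required, they were 8% to 30% as planned. The plan does not say which association counts.

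**Stronger readings to avoid.** A reader might infer that all three variables are raw differences. That is wrong for VT and unstated for the other two. A reader might also infer that one in four positive results would be false. The 24% is the worst row of one table, conditional on inputs that the documents do not give. Finally, adjustment does not restore nominal error: any-direction rates with baselines remain about 7% to 9.5% in Simulation A with the bias-corrected interval.

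**Conclusion.** The omission is real. The LPS mediation model lists no pre-LPS value, while the plan adjusts for pre-LPS VT in Aim 2 and expects the starting levels to be correlated. An apparent indirect effect can therefore be created or hidden through baseline.

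The size is conditional. With n = 80, no true VT-change-to-symptom-change effect, an additive increment, r0 from 0.39 to 0.60 and rS from -0.3 to -0.5, positive mediation is called in about 8% to 24% of trials as planned and about 2% to 5% with baselines, against a nominal 2.5%. There is no inflation under a proportional increment, and masking or wrong-direction calls if symptom change rises with baseline. The documents do not show which case applies. This affects the interpretation of Aim 3(b) only; it does not touch the group comparisons of Aims 1 and 2. It should be changed because the remedy is cheap and did no harm in the cases tried.

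**What to change.** In Section I, item 13, Aim 3 paragraph:
- Enter the pre-LPS marker, pre-LPS global VT, the pre-LPS symptom or cognition score, and rs6971 genotype as covariates in both the mediator and the outcome equation of the LPS mediation models. Genotype belongs there because the protocol reports a roughly two-fold baseline VT difference between high and medium binders.
- Adjust the partial correlations among LPS-induced measures for the same baselines.
- State the scale of the marker and symptom changes, and which association admits a marker to the mediation step.

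Modelling post-LPS values with the pre-LPS values as covariates, with VT on the log scale, is an acceptable alternative. It is not the same model as percent change, so one should be named in advance.

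The cost is a sentence or two of text and about four degrees of freedom out of 80: three baselines, plus one for genotype because low binders are excluded. The protocol already collects VT, cytokines, symptoms and cognition before LPS, so no new data are needed.

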# A. RADIOTRACERS

- 1. Name of the radiotracer: [C]PBR28 or *N*-acetyl-*N*-(2-[C]methoxybenzyl)-2-phenoxy-5pyridinamine
- 2. Is the radiotracer FDA approved? **YES XNO**

If NO, an FDA issued IND is required for the investigational use unless RDRC assumes oversight.

- 3. Check one:  $\square$  IND# 123984 or  $\square$  RDRC oversight (RDRC approval will be required prior to use)
- 1a. Name of the radiotracer: [18F]FDG or [18F]2-Fluro-deoxyglucose (2-deoxy-2-[18F]fluoro-D-glucose
- 1b. Is the radiotracer FDA approved? **VYES DNO**

# B. DRUGS/BIOLOGICS

- 1. If an **exemption from IND filing requirements is** sought for a clinical investigation of a drug product that is lawfully marketed in the United States, review the following categories and complete the category that applies (*and delete the inapplicable categories*):
- 2. **Background Information:** Provide a description of previous human use, known risks, and data addressing dosage(s), interval(s), route(s) of administration, and any other factors that might influence risks. If this is the first time this drug is being administered to humans, include relevant data on animal models.

*PET tracer:* [F]FDG tracer will be administered i.v. in doses of 10 mCi or less

*PET tracer*: [C]PBR28 tracer will be administered i.v. in doses of 20 mCi or less for aim 4, doses of 18mci or less for aims 1, 2, and 5.

#### Endotoxin

In 1976, endotoxin derived from *E. coli* (group O 113:H10:K negative) was processed to serve as a national standard for experimental studies of inflammation in humans. When this lot was depleted in 1998, the NIH Clinical Center in conjunction with FDA processed, under good-manufacturing-practice guidelines, endotoxin derived from the original bulk material extracted from *E. coli* O:113. This Clinical Center Reference

Page 29 of 45

Endotoxin (CCRE) has been used in multiple human research studies since then. CCRE is an investigational drug, and the PI has been allowed by FDA to use it in humans under an IND (BB IND#13598). Each vial produced by List Labs, when reconstituted with 0.5 ml water, contains 1 microgram of endotoxin in 1.0% lactose, 0.1% PEG6000.This product has been manufactured according to cGMP using procedures compliant with 21 CFR 211. All specifications and lot disposition requirements have been met.This product is supplied as lyophilized powder, aseptically filled into depyrogenated, sterile, 2 ml glass vials and sealed under vacuum. It is recommended that this material be stored at 2 - 8°C prior to and after reconstitution. Prior to using LPS, vortex for 15 minutes after reconstitution with sterile water for injectionVials should be stored refrigerated and reconstituted in 5 cc of Sterile Water for Injection at the time of use. CCRE is administered intravenously or by lung instillation through bronchoscopy. The most commonly used dose is 2-4 ng/kg body weight by IV bolus. Preparation of the standardized CCRE will be performed by our clinical research pharmacist.

3. **Source:** Identify the source of the drug or biologic to be used.

[11C]PBR28 Radiotracer will be synthesized and radiolabeled by the Yale University PET Center under the supervision of Drs. [name] and [name].

Endotoxin (CCRE) will be provided by the List Labs and shipped to the Investigational Drug Pharmacy.

[18F]FDG will be produced and shipped to the Yale University PET Center by an approved vendor.

a) Is the drug provided free of charge to subjects? **XYES INO** If yes, by whom? *Write here* 

1. **Storage, Preparation and Use:** Describe the method of storage, preparation, stability information, and for parenteral products, method of sterilization and method of testing sterility and pyrogenicity.

Due to the short half-life, PET drugs are prepared and formulated immediately before administration, and therefore there are no issues with storage or stability. PET drug products are stored at room temperature and are stable for at least 60 min after preparation.

The preparation of sterile PET drug products is validated prior to human use. Sterility is achieved by passing the PET drug product through a 0.22 micron membrane filter during the last step in the formulation process. Prior to release for administration, a bubble point test is performed on the membrane filter used for terminal sterilization in order to validate and verify its integrity during the filtration process. Due to the short half-life, a sample of the PET drug product is tested for sterility after administration for further confirmation.

The level of endotoxin in each batch of the final PET drug product is determined quantitatively prior to release for administration using the FDA approved Charles River Laboratory's Portable Testing System (Endosafe®-PTS).

# [C]PBR28

[C]PBR28 will be prepared at the Yale PET Center in accordance with procedures and quality specifications described in Yale IND # 123984.Briefly, [C]PBR28 is radiolabeled by *O*-methylation of the phenolic group of the *O*-desmethyl-precursor with [C]methyl iodide or [C]methyl triflate. The PET drug is purified first by semi-preparative HPLC, and then followed by solid-phase extraction to remove the HPLC buffer mixture. Finally, the

Page **30** of **45** 

PET drug is formulated in <10% ethanolic saline solution, and the resulting PET drug product is finally passed through a 0.22 micron membrane filter for terminal sterilization.

#### FDG

[18F]FDG will be produced and shipped to the Yale University PET Center by an approved vendor and will be administered immediately upon receipt at the Yale PET Center.

#### Endotoxin

Preparation and storage of CCRE will be done by the YNHH IDS pharmacy, according to the recommendations by the NIH Clinical Center and List Labs. CCRE is inherently pyrogenic and will therefore not be tested for pyrogenicity.

### Check applicable Investigational Drug Service utilized:

**VNHH IDS** 

**CMHC** Pharmacy □ None

U West Haven VA

🛛 Radio

□ Telephone

⊠ Television

⊠ Newspaper

□ Clinicaltrails.gov

PET Center

□ Other:

**Note:** If the YNHH IDS (or comparable service at CMHC or WHVA) will not be utilized, explain in detail how the PI will oversee these aspects of drug accountability, storage, and preparation.

#### 2. Use of Placebo: Not applicable to this research project

- 3. Continuation of Drug Therapy After Study Closure 🛛 Not applicable to this project
- ⊠N/A **B. DEVICES**

SECTION III: RECRUITMENT/CONSENT AND ASSENT PROCEDURES

### 1. Targeted Enrollment: Give the number of subjects:

- a. Targeted for enrollment at Yale for this protocol: 160 total
- b. If this is a multi-site study, give the total number of subjects targeted across all sites: Write here

### 2. Indicate recruitment methods below. Attach copies of any recruitment materials that will be used.

⊠ Flyers

□ Letter

- ⊠ Internet/web postings
- □ Posters □ Mass email solicitation
  - ⊠ Departmental/Center website
    - □ Departmental/Center research boards
    - □ Web-based clinical trial registries
- ☑ Departmental/Center newsletters □ YCCI Recruitment database
  - Social Media (Twitter/Facebook):

□ Other:

# \* Requests for medical records should be made through JDAT as described at

http://medicine.yale.edu/ycci/oncore/availableservices/datarequests/datarequests.aspx

# 3. Recruitment Procedures:

□ Medical record review\*

- a. Describe how potential subjects will be identified. Write here
- b. Describe how potential subjects are contacted. Write here
- c. Who is recruiting potential subjects? Write here

Page 31 of 45

### APPROVED BY THE YALE UNIVERSITY IRB 12/20/2022

Subjects will be recruited through flyers and business cards, public advertisement (newspaper, radio, internet posting), by word of mouth, contact with community service groups, and clinics and local treatment facilities (the VA Hospital, West Haven, CMHC, the Yale Psychiatric Hospital, Mood Disorders Research Program, the Yale Depression Research Program, CTNA). The subjects will be asked to call us if they are interested in participating in the research study. Trained RA's, under direct supervision of the PI, are responsible for subject recruitment.

### 4. Assessment of Current Health Provider Relationship for HIPAA Consideration:

Does the Investigator or any member of the research team have a direct existing clinical relationship with any potential subject?

□Yes, all subjects □Yes, some of the subjects ⊠No

If yes, describe the nature of this relationship. Write here

**5. Request for waiver of HIPAA authorization:** (When requesting a waiver of HIPAA Authorization for either the entire study, or for recruitment purposes only. Note: if you are collecting PHI as part of a phone or email screen, you must request a HIPAA waiver for recruitment purposes.)

### Choose one:

 $\Box$  For entire study

☑ For recruitment/screening purposes only

□ For inclusion of non-English speaking subject if short form is being used and there is no translated HIPAA research authorization form available on the University's HIPAA website at hipaa.yale.edu.

i. Describe why it would be impracticable to obtain the subject's authorization for use/disclosure of this data: We post advertisements in which subjects are asked to call us if they are interested in participating in the studies. When the subjects call, we need to obtain their name, DOB, phone number, etc, in order to contact them regarding eligibility to participate/schedule further appointments, assess study eligibility correctly. Some subjects prefer we email them appointments and directions; thus we need to obtain their email address. We also need to obtain their city of residence to ensure they are within appropriate distance to arrive to all appointments in a timely fashion and to provide accurate directions to our labs.

The investigator assures that the protected health information for which a Waiver of Authorization has been requested will not be reused or disclosed to any person or entity other than those listed in this application, except as required by law, for authorized oversight of this research study, or as specifically approved for use in another study by an IRB.

Researchers are reminded that unauthorized disclosures of PHI to individuals outside of the Yale HIPAA-Covered entity must be accounted for in the "accounting for disclosures log", by subject name, purpose, date, recipients, and a description of information provided. Logs are to be forwarded to the Deputy HIPAA Privacy Officer.

6. Process of Consent/Assent: Describe the setting and conditions under which consent/assent will be obtained, including parental permission or surrogate permission and the steps taken to ensure subjects' independent decision-making.

Potential subjects will initially be screened over the telephone by one of the research staff. The study will be described to individuals who appear to satisfy the study criteria. During an intake appointment, the nature

Page 32 of 45

of the project, the procedures, the relative risks and benefits, and the alternatives to participation in the project will be discussed with the subject. If, following this discussion, the subject continues to be interested in the project; written informed consent will be obtained. The decision not to participate will not affect an individual's eligibility to participate in future studies, to receive treatment at the Connecticut Mental Health Center, or to receive treatment on a private basis from a referring clinician. A copy of the signed consent form will be provided to all participating subjects.

7. Evaluation of Subject(s) Capacity to Provide Informed Consent/Assent: Indicate how the personnel obtaining consent will assess the potential subject's ability and capacity to consent to the research being proposed.

In cases in which capacity is in doubt, the PI will assess the subject's understanding of the study and the subject's capacity to decide to participate.

8. Non-English Speaking Subjects: Explain provisions in place to ensure comprehension for research involving non-English speaking subjects. If enrollment of these subjects is anticipated, translated copies of all consent materials must be submitted for approval prior to use.

Non-English speaking subjects will not be invited to participate in the studies. All of our materials are in English only, and staff members are fluent in English. Furthermore, cognitive testing is validated in English-speaking subjects only.

As a limited alternative to the above requirement, will you use the short form\* for consenting process if you unexpectedly encounter a non-English speaking individual interested in study participation and the translation of the long form is not possible prior to intended enrollment? YES  $\Box$  NO  $\boxtimes$ 

Note\* If more than 2 study participants are enrolled using a short form translated into the same language, then the full consent form should be translated into that language for use the next time a subject speaking that language is to be enrolled.

Several translated short form templates are available on the HRPP website (yale.edu/hrpp) and translated HIPAA Research Authorization Forms are available on the HIPAA website (hipaa.yale.edu). If the translation of the short form is not available on our website, then the translated short form needs to be submitted to the IRB office for approval via modification prior to enrolling the subject. *Please review the guidance and presentation on use of the short form available on the HRPP website.* 

If using a short form without a translated HIPAA Research Authorization Form, please request a HIPAA waiver in the section above.

9. Consent Waiver: In certain circumstances, the HIC may grant a waiver of signed consent, or a full waiver of consent, depending on the study. If you will request either a waiver of consent, or a waiver of signed consent for this study, complete the appropriate section below.

⊠Not Requesting any consent waivers

Page **33** of **45** 

